### **3.3 Rationale of dose/regimen, route of administration and duration of treatment**

The dose, dose regimen, titration scheme and tapering-off scheme, etc. are in accordance with product labeling.

### **3.4 Rationale for choice of comparator**

A comparator arm is not applicable for this study

### **3.5 Purpose and timing of interim analyses/design adaptations**

Not applicable

### **3.6 Risks and benefits**

The risk to subjects in this trial will be minimized by compliance with the inclusion/exclusion criteria, close clinical monitoring, and minimal study duration which will be planned as 1,5 years enrollment time and 6 months follow up.

## **4 Population**

The study will include only 80 relapsing remitting MS patients and 60 healthy controls without any known autoimmune disease. RRMS patients will be followed for 6 months.

### **4.1 Inclusion criteria**

1. Written informed consent must be obtained before any assessment is performed.
2. RRMS patients aged between 18-65 years that fulfill following criteria:
  - d) In non-treated/newly-diagnosed patients with two or more serious attacks within one year or three or more serious attacks within two years and one or multiple gadolinium-enhancing lesions in cranial MRI or with significantly increased T2 lesions compared to the previous MRI.
  - e) In non-responders despite treatment with a beta-interferon or glatiramer acetate with adequate duration and dose, where:
    - a. adequate treatment duration is at least 1 year and,
    - b. non-responders are patients with no changes in attacks or increased number of attacks after one year of treatment, or with more severe attacks, or those with one or multiple contrast enhancing lesions in cranial MRI or where there is an increase in T2 lesions identified with successive MRI's.
  - f) In RRMS patients who are unable to tolerate first-line treatments due to adverse effects associated with parenteral administration.
3. Last relapse of the patient should be at least 2 months before study entry.
4. Last steroid dose of the patient should be at least 1 month before study entry.

5. Last interferon or glatiramer acetate dose of the patient should be at least 1 month before study entry.
6. Last cyclophosphamide, mitoxantrone, teriflunamide, natalizumab and azathioprine dose of the patient should be at least 3 months before study entry.

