### **4.2 Exclusion criteria**

Patients fulfilling **any** of the following criteria are not eligible for inclusion in this study. No additional exclusions may be applied by the investigator, in order to ensure that the study population will be representative of all eligible patients.

1. Patients with secondary progressive MS.
2. Patients with known contraindications for fingolimod treatment.
3. Other coexistent autoimmune diseases including Hashimoto thyroiditis, systemic lupus erythematosus, rheumatoid arthritis, psoriasis etc.
4. Patients with any of the following cardiovascular conditions:
  - Resting heart rate < 45 bpm/min
  - Cardiac failure at any time during the first study visit (Class III as per NYHA classification) or significant heart disease as judged by the physician
  - Myocardial infarction during the last 6 months
  - History of Mobitz Type II grade 2 AV block
  - Past or current grade 3 AV block
  - Confirmed history of sick sinus syndrome or sino-atrial heart block
  - arrhythmia requiring current treatment with Class Ia drugs (ajmaline, disopyramide, procainamide, quinidine)
  - hypertension uncontrolled with medication
5. History of malignancy of any organ system other than localized basal cell carcinoma of the skin
6. Pregnant or nursing (lactating) women
7. Negative for varicella-zoster virus IgG antibodies at screening
8. History of previous fingolimod therapy

9. Presence of any clinically active infections

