#### **5.4.8 Prohibited Treatment**

Use of the following treatments is NOT allowed concomitantly with the study drug during the course of the study: (use can only be considered if the study drug is permanently discontinued):

- Immunosuppressive medication (e.g. cyclosporine, azathioprine, methotrexate, cyclophosphamide, mitoxantrone, cladribine);
- Other concomitant medications: immunoglobulins, monoclonal antibodies (including natalizumab), INF- $\beta$ , glatiramer acetate, adrenocorticotropic hormone (ACTH). The administration of any live or live attenuated vaccines (including for measles) is prohibited while patients are receiving study drug and for 3 months after study drug discontinuation. They may be administered, thereafter, once there is confirmation that lymphocyte counts are in the laboratory normal range. Use of the following treatments is allowed to manage potential adverse reactions associated with the study drug:
  - i. anticholinergics (atropine s.c. or i.v.) for treatment of symptomatic bradycardia as the first line treatment, up to 3 mg/day;
  - ii. beta-agonists/sympathomimetics (dopamine drip 5-20 $\mu$ g/kg/min or epinephrine drip 2- 10  $\mu$ g/min) for treatment of non-responsive bradycardia. Standard short course of corticosteroids (methylprednisolone i.v.) is allowed for treatment of relapses.

The medications allowed for treatment of adverse reactions and relapses are not considered study supplies, and therefore, need to be supplied by the study site. The investigator should instruct the patient to notify the study site about any new medications he/she takes after the start of the study drug.

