## **6.1 Information to be collected on screening failures**

Since the study is aiming to collect serum samples from the MS patients and healthy volunteers, screening visit is not applicable. The investigators will assess the inclusion/exclusion criteria in visit 1 and the patients who are not eligible for the study will not give any serum samples. There is no information to be collected for screen failures.

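### Several treatments prohibited with study drug have no pre-entry washout, so a few recently exposed patients may be sampled and dosed on Day 0

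*Protocol*

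**What the plan says.** Protocol 4.1 sets pre-entry intervals for a closed list. Criterion 4: "Last steroid dose of the patient should be at least 1 month before study entry". Criterion 5 gives interferon and glatiramer the same 1 month. Criterion 6: "Last cyclophosphamide, mitoxantrone, teriflunamide, natalizumab and azathioprine dose of the patient should be at least 3 months before study entry". The synopsis repeats all three.

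Protocol 5.4.8 covers the treatment period: "Use of the following treatments is NOT allowed concomitantly with the study drug during the course of the study". Its first group is "Immunosuppressive medication (e.g. cyclosporine, azathioprine, methotrexate, cyclophosphamide, mitoxantrone, cladribine", an open list. Its second group begins "Other concomitant medications: immunoglobulins, monoclonal antibodies (including natalizumab" and goes on to interferon beta, then "glatiramer acetate, adrenocorticotropic hormone (ACTH".

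On timing, section 6.1 says there is no screening visit and that "The investigators will assess the inclusion/exclusion criteria in visit 1". Table 6-1 puts the eligibility check, the baseline biomarker sample and the first dose at Visit 1, Day 0. Section 4.2 adds that "No additional exclusions may be applied by the investigator".

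**The concern.** The washout list and the prohibition list do not match. Of the six immunosuppressants that 5.4.8 names, three have a 3-month washout and three have none. Natalizumab has 3 months, while the rest of the antibody class has nothing. No reason is given for the split.

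Two things are at stake.

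- **Baseline.** The Visit 1 sample enters three of the four planned contrasts for every ELISA and flow cytometry analyte (SAP 6.5.1 and 6.5.2): against controls, and as the reference for change at Visits 2 and 3. The planned tests are unadjusted, so eligibility is the main protection against residual drug effects on cytokines. The protocol accepts the principle, both in criteria 4 to 6 and in section 5.4.6, which postpones blood sampling until a month after a corticosteroid course.
- **Safety.** Section 1.1 warns that combining fingolimod with other immunosuppressants may raise the infection risk further. Section 3.6 names the entry criteria among its means of keeping risk low.

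**Working it through.** **Comparing the lists**

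| Treatment in Protocol 5.4.8 | Pre-entry interval in 4.1 |
|---|---|
| Azathioprine, cyclophosphamide, mitoxantrone | 3 months (criterion 6) |
| Natalizumab | 3 months (criterion 6) |
| Interferon beta, glatiramer | 1 month (criterion 5) |
| Cyclosporine | none |
| Methotrexate | none |
| Cladribine | none |
| Immunoglobulins | none |
| Monoclonal antibodies other than natalizumab | none |
| ACTH | none (criterion 4 says steroid; 5.4.8 lists ACTH by name) |

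Six named agents or classes have no interval. Because the immunosuppressant list is open, unnamed agents fall in the gap too.

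**Does another provision close it?**

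- Section 5.4.8 bars use together with study drug. It does not reach a drug stopped the day before.
- Section 4.2 has no exclusion for recent immunosuppressive or antibody therapy, and it stops the investigator from adding one.
- Exclusion 2 (contraindications to fingolimod) may catch some patients, but the documents do not list the contraindications and it states no interval.
- The entry routes for first-line non-responders and for patients intolerant of first-line treatment do not rule out later use of one of these drugs.

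**The plan's own figure**

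Inputs from Protocol 9.8: SD 15 pg/ml, paired difference 7 pg/ml, alpha 0.05 (taken as two-sided), power 90%. Treating 15 as the SD of the paired difference:

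n = ((1.960 + 1.282) × 15 / 7)² = 48.2, rounded up to 49 pairs.

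The exact paired t test with 50 pairs has power 0.899. The stated 50 pairs therefore reproduces. This point does not depend on it; it supplies only the scale for what follows.

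**Sensitivity of the MS mean**

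The documents give neither an exposure rate nor the effect of residual drug on IL-17, so the shift *d* (in SD units) is assumed. With 60 patients (9.8), one affected patient moves the mean by d × 15 / 60.

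| Assumed d | Shift per patient (pg/ml) | Share of 7 pg/ml |
|---|---|---|
| 0.5 | 0.125 | 1.8% |
| 1.0 | 0.25 | 3.6% |
| 1.5 | 0.375 | 5.4% |

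At 1 SD, moving the mean by the full 7 pg/ml would take 7 / 0.25 = 28 of 60 patients.

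For several patients, suppose 1 to 4 of 60 are exposed and each is shifted by 7 to 15 pg/ml. The mean moves by between 1 × 7 / 60 = 0.12 and 4 × 15 / 60 = 1.0 pg/ml, or 1.7% to 14% of 7. If every shift shrinks the difference, paired power at 50 pairs falls from 0.90 to between 0.89 and 0.79. The lower end needs four patients, each off by a full SD in the unfavourable direction.

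**The case against.** The best case against acting is that the two lists do different jobs. Section 5.4.8 is a broad prohibition during treatment, while criteria 4 to 6 target the drugs that the entry routes make likely. Those routes admit untreated patients, first-line non-responders and first-line intolerant patients, none of whom typically arrives by way of cyclosporine, methotrexate, cladribine or immunoglobulins. Exclusions 3 and 5 remove patients with other autoimmune disease or with most malignancies, and criterion 3 (2 months since the last relapse) limits recent ACTH given for a relapse. Concomitant drugs are checked again before the first dose (5.4.4), MS treatment history is recorded (6.2), and the SAP tabulates previous MS treatment (6.2).

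The effect is also small. With 80 patients in place of 60, the per-patient shift falls to 7.5 / 80 = 0.09 up to 22.5 / 80 = 0.28 pg/ml (1.3% to 4.0% of 7). Where the SAP uses rank tests, one patient's influence is bounded and a mean shift does not describe it. The 5.4.6 sampling rule concerns rescue steroids on study, so it is only a loose parallel. Finally, nothing in the documents supports 3 months for every agent.

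Much of this stands. The patients are probably few, the mean-shift figures only indicate scale, and the 5.4.6 rule shows a principle, not a missing twin. The 3 months is borrowed from criterion 6 and is a floor. What does not stand is that the gap is closed: none of these provisions sets a washout. A table of previous treatment shows exposure after the event but keeps nobody from being sampled or dosed. The safety point cannot be sized, because the contraindications are not listed, but it concerns each exposed patient and does not depend on how many there are.

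**Conclusion.** The concern holds, at low severity. As written, the entry criteria let a patient recently exposed to any of six named agents or classes give the baseline sample and take the first dose on Day 0, unless the unlisted contraindications happen to exclude that patient. The effect on the control contrast is probably small and none is demonstrated. The sizes given rest on an assumed shift of 0.5 to 1.5 SD, on 60 patients, and on the protocol's SD for IL-17 alone; the other analytes have no stated SD. Confidence is medium: the gap in the text is certain, but the number of patients it would admit is unknown.

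**What to change.** - Keep criterion 6 with its five drugs and 3 months. Add cyclosporine, methotrexate, cladribine, other immunosuppressants, immunoglobulins and any other monoclonal antibody, at the same 3-month minimum or longer where the sponsor specifies.
- Add ACTH to the 1-month steroid rule in criterion 4.
- Make the same two changes in the synopsis.

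Sample size, visit schedule and planned tests are unchanged. The cost is a written amendment with the approvals in Protocol 11.1, and a few patients who are delayed or become ineligible.

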### **Inclusion Criteria for Healthy Control Group**

3. Healthy people who don't have MS and aged >18.
4. Written informed consent must be obtained before any assessment is performed.

### **4.2 Exclusion criteria**

Patients fulfilling **any** of the following criteria are not eligible for inclusion in this study. No additional exclusions may be applied by the investigator, in order to ensure that the study population will be representative of all eligible patients.

1. Patients with secondary progressive MS.
2. Patients with known contraindications for fingolimod treatment.
3. Other coexistent autoimmune diseases including Hashimoto thyroiditis, systemic lupus erythematosus, rheumatoid arthritis, psoriasis etc.
4. Patients with any of the following cardiovascular conditions:
  - Resting heart rate < 45 bpm/min
  - Cardiac failure at any time during the first study visit (Class III as per NYHA classification) or significant heart disease as judged by the physician
  - Myocardial infarction during the last 6 months
  - History of Mobitz Type II grade 2 AV block
  - Past or current grade 3 AV block
  - Confirmed history of sick sinus syndrome or sino-atrial heart block
  - arrhythmia requiring current treatment with Class Ia drugs (ajmaline, disopyramide, procainamide, quinidine)
  - hypertension uncontrolled with medication
5. History of malignancy of any organ system other than localized basal cell carcinoma of the skin
6. Pregnant or nursing (lactating) women
7. Negative for varicella-zoster virus IgG antibodies at screening
8. History of previous fingolimod therapy

9. Presence of any clinically active infections

## **5 Treatment**

### **5.1 Protocol requested treatment**

#### **5.1.1 Investigational treatment**

Treatment will be 0.5 mg p.o fingolimod daily for the treatment arm. The study drug will be provided by Novartis .

Control group will not receive any treatment.

#### **5.1.2 Additional study treatment**

No additional treatment beyond investigational treatment is requested for this trial.

### **5.2 Treatment arms**

Not Applicable.

### **5.3 Treatment assignment, randomization**

Not Applicable.

### **5.4 Treating the patient**

#### **5.4.1 Patient numbering**

Each patient is uniquely identified by a Subject Number which is composed by the site number assigned by Novartis and a sequential number assigned by the investigator. Once assigned to a patient, the Subject Number will not be reused.

Upon signing the informed consent form, the patient is assigned the next sequential number as given by the investigator using the next blank CRF book.

#### **5.4.2 Dispensing the investigational treatment**

Each study site will be supplied by Novartis with investigational treatment in packaging of identical appearance.

The investigational treatment packaging has a 2-part label. A unique medication number is printed on each part of this label which corresponds to the treatment. Investigator staff will select the investigational treatment to dispense to the patient using the *visit number* on the label. Immediately before dispensing investigational treatment to the patient, investigator staff will detach the outer part of the label from the packaging and affix it to the source document (Drug Label Form) for that patient's unique patient number.

## 5.4.3 Handling of study treatment

### 5.4.3.1 Handling of investigational treatment

Investigational treatment must be received by a designated person at the study site, handled and stored safely and properly, and kept in a secured location to which only the investigator and designees have access. Upon receipt, all investigational treatment should be stored according to the instructions specified on the labels. Clinical supplies are to be dispensed only in accordance with the protocol.

Medication labels will be in the local language and comply with the legal requirements of each country. They will include storage conditions for the investigational treatment but no information about the patient except for the visit number.

The investigator must maintain an accurate record of the shipment and dispensing of investigational treatment in a drug accountability log. Monitoring of drug accountability will be performed by the field monitor during site visits and at the completion of the trial. Patients will be asked to return all unused investigational treatment and packaging at the end of the study or at the time of discontinuation of investigational treatment.

At the end of the study, and as appropriate during the course of the study, the investigator will return all unused investigational treatment, packaging, drug labels, and a copy of the completed drug accountability log to the Novartis monitor or to the Novartis address provided in the investigator folder at each site.

Handling of other study treatment

Not applicable.

## 5.4.4 Administering study treatment

Prior to administration of the first dose of the study drug the investigator should reconfirm a list of concomitant medications taken by the patient. It is recommended not to initiate treatment with beta-blockers, calcium-channel blockers or digoxin within one week before or after the first dose of the study drug due to a possible additive effect on heart rate reduction.

The first dose of the study drug must be administered under the supervision of the First Dose Administrator or designee. It is recommended that the first dose be administered in the morning time, before 12:00 noon. The patient will stay at the study center for a minimum of 6 hours. Heart rate and blood pressure will be monitored hourly during the six hour stay and discharged if specific discharge criteria are met. Hourly monitoring will be extended if the discharge criteria are not met. Some patients may be required to return to the study center for 6 hours following the 2nd dose.

The investigator and/or study personnel should promote compliance by instructing the patient to take one capsule of the study drug orally once daily with or without a meal, preferably at the same time each day and by stating that compliance is necessary for the patient's safety and validity of the study. The patient should be instructed to contact the site if he/she is unable for any reason to take the study drug .

## 5.4.5 Permitted dose adjustments and interruptions of study treatment

Dose adjustments will not be allowed, however drug interruptions will be allowed based on

Conditions/events that may lead to the study drug interruptions based on investigator judgment and overall clinical assessment:

- reported serious adverse event;
- emergency medical condition, unplanned hospitalization, involving use of excluded concomitant medications;
- abnormal laboratory value(s) or abnormal test or examination result(s) (e.g. PFT, liver function tests, ophthalmic findings etc.).
- patient's non-compliance.

Should the patient interrupt the study drug, and should the investigator decide in agreement with the sponsor to re-initiate treatment with the study drug, depending on the duration of the interruption (see below), the first dose at re-start may need to take place under supervision of the First Dose Administrator in a similar manner as the first intake of the study medication. It is recommended not to initiate beta-blockers, calcium-channel blockers or digoxin treatment within one week before or after the day of re-initiation of the study drug administration due to a possible additive effect on heart rate reduction.

When re-starting of study drug monitoring (as for first dose) is mandatory in the following cases:

- The treatment lasted for less than 8 days and was interrupted for more than 1 day
- The treatment lasted for 8 days or more and was interrupted for 8 days or more

Re-start decision should be made on a case by case basis and should be discussed with the Medical Advisor at Novartis. A reason for the interruption of treatment and time of interruption should be appropriately documented in the source documents as well as in the Dosage Administration Record CRF. All required guidelines for the above matters are given as an appendix to this protocol

#### **5.4.6      Rescue medication**

A standard course of corticosteroids (methylprednisolone) on an inpatient or outpatient basis is allowed for treatment of relapses as clinically warranted.

Steroid treatment should consist of 3-5 days and up to 1,000 mg methylprednisolone/day. Standard of care procedures will be followed during treatment.

Use of any oral tapering is not permitted.

The use of steroid therapy should be recorded in the related section of CRF.

Investigators should consider the added immunosuppressive effects of corticosteroid therapy and increase vigilance regarding infections during such treatment and in the weeks following administration.

Patients should be reminded of the importance of reporting any signs or symptoms of an infection during treatment. Special consideration should be given to symptoms or signs of herpes simplex or zoster reactivation (e.g. lancinating pain, skin lesions) and appropriate antiviral therapy (e.g. acyclovir, valacyclovir) should be promptly initiated and continued for up to 30 days after stopping high dose steroid treatment. An infectious disease specialist may be consulted to guide such therapy if needed.

Should a patient develop any neurological symptoms or signs, unexpected for MS in the opinion of the investigator or accelerated neurological deterioration, the investigator should immediately schedule an MRI and follow the “Guidance on monitoring of patients with symptoms or signs of neurological deterioration inconsistent with MS”. Steroids should not be taken prior to conducting the unscheduled MRI.

If the patient is currently under treatment with corticosteroids, the blood sample should be obtained at least 1 month after the end of the corticosteroid treatment.

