**Table 6-2 Assessment schedule for Healthy Control Group**

Visit	1	2	3
Day	0	90±7	180±14
Obtain Informed Consent	X		
Evaluation of Inclusion/Exclusion Criteria	X		
Collecting Serum and Blood Samples	X		

Patients should be seen for all visits on the designated day with an allowed “visit window” of “7” days at visit 2 and “14” days at visit 3 , or as close to it as possible, or as shortly after it as possible, or as shortly before it as possible, etc.

At a minimum, patients will be contacted for safety evaluations during the 30 days following the last study visit or following the last administration of study treatment if there are post-treatment follow-up visits (whichever is later), including a final contact at the 30-day point. Documentation of attempts to contact the patient should be recorded in the source documentation.

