6.5 ASSESSMENT OF CYTOKINE AND CHEMOKINE LEVELS

6.5.1 ELISA

Subjects' **IL-4, IL-6, IL-8, IL-9, IL-10, IL-13, IL-17, IL-23, IFN- γ , TNF- α , VLA4, CCL2, CCL5, CXCR3 and CXCL13** values will be tabulated by calculating mean and standart error and compared as Control group vs. Visit 1 (MS patients), Visit 1 (MS patients) vs. Visit 2 (MS patients), Visit 1 (MS patients) vs. Visit 3 (MS patients) and Control group vs. Visit 3 (MS patients) by using appropriate statistical test. Mann Whitney U test with significance level of 0.05 was used for the independent variables since non-normal distributions had been observed. Wilcoxon test was used for the dependent variables with non-normal distributions. For the independent variables with normal distributions Independent Sample t test was used whereas Paired sample t test was used for the dependent variables with normal distributions.

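### The on-study steroid deferral rule covers only patients on corticosteroids at the visit, so samples taken within a month after a course enter the Visit 2 and Visit 3 comparisons unmarked

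*Protocol*

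**What the plan says.** At baseline, the inclusion criteria in Protocol 4.1 require that "Last steroid dose of the patient should be at least 1 month before study entry".

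During follow-up, Protocol 5.4.6 says that a standard course of methylprednisolone "is allowed for treatment of relapses as clinically warranted", and that "Steroid treatment should consist of 3-5 days and up to 1,000 mg methylprednisolone/day". Oral tapering is not permitted, and steroid use is to be recorded on the CRF. The same section ends with the sampling rule: "If the patient is currently under treatment with corticosteroids, the blood sample should be obtained at least 1 month after the end of the corticosteroid" course. No other passage makes a Visit 2 or Visit 3 sample depend on steroid exposure.

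On timing, the text under Table 6-2 says: "Patients should be seen for all visits on the designated day with an allowed “visit window” of “7” days at visit 2 and “14” days" for the last visit. It then allows a visit as near to the designated day as can be managed, before or after.

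For analysis, SAP 6.5.1 and 6.5.2 compare controls with Visit 1, then "Visit 1 (MS patients) vs. Visit 2 (MS patients), Visit 1 (MS patients) vs. Visit 3 (MS patients"), and controls with Visit 3. SAP section 6 takes all MS patients and controls as the analysis sets. Neither document flags, adjusts for or excludes samples after recent steroids, and Protocol 9.6 lists supportive analyses as not applicable.

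**The concern.** The protocol uses one month off steroids as its standard twice: to admit a patient to baseline sampling, and as the waiting time once the deferral rule applies. The trigger for that rule is much narrower than the standard. It depends on the patient being on steroids at the time of the visit, which with a 3-5 day course and no taper is a matter of days. A patient one day past the last infusion would not have qualified for the baseline sample, yet gives the follow-up sample on schedule.

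The within-patient contrasts are the plan's only test of whether fingolimod changes cytokine levels, and Protocol 3.2 rests its claim of no bias on patients serving as their own controls. That needs comparable sampling conditions at each visit. Protocol 5.4.6 itself recognises added immunosuppression from steroids, with vigilance extending into the weeks after a course. A steroid-driven change in a follow-up sample would be read as a drug effect.

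The affected samples come from patients who relapsed, so the error is not random with respect to relapse. The secondary objective relates these same cytokine changes to relapse rate, although the SAP specifies no analysis for that association.

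**Working it through.** **The plan's own figure.** Protocol 9.8 and SAP 5.1 give 50 pairs for a 7 pg/ml IL-17 difference, SD 15 pg/ml, alpha 0.05 and power 90%. Taking 15 as the SD of the paired difference and a two-sided test, n = (15 × (1.960 + 1.282) / 7)² = 48.2, rounded up to 49. Exact noncentral-t power at 50 pairs is 89.9%. The figure reproduces. It serves here only as a yardstick for size.

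**Days the rule catches.** Take one month as 30 days. A course of c days leaves c + 30 days on which a sample falls short of the one-month standard. The literal trigger catches only the c course days:

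- 3-day course: 3/33 = 9%
- 5-day course: 5/35 = 14%

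The 30 days after the course are uncaught (91% and 86%). These are shares of calendar days, not a measure of bias.

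**Patients affected at one visit.** The documents give no on-treatment relapse rate, so rates r per patient-year are assumed, relapses are taken to occur at a constant rate, and every relapse is taken to be treated. The share in the uncaught period is p = 1 − exp(−r × 30/365). The count uses 60 patients, the minimum enrolment in the sample size section. The mean shift is 15 × p, assuming that each affected sample moves by one SD (15 pg/ml).

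| Assumed r | p | Of 60 | Shift in mean IL-17 (pg/ml) |
|---|---|---|---|
| 0.1 | 0.8% | 0.5 | 0.12 |
| 0.2 | 1.6% | 1.0 | 0.24 |
| 0.5 | 4.0% | 2.4 | 0.60 |
| 1.0 | 7.9% | 4.7 | 1.18 |

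A 2-SD shift per affected sample would double the last column, to at most about 2.4 pg/ml. The planned difference is 7 pg/ml.

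**Which contrasts are exposed.** Visit 1 vs 2, Visit 1 vs 3 and Control vs Visit 3 all use follow-up samples. Control vs Visit 1 uses only samples covered by the entry criteria.

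**Deferral against the visit windows.** Table 6-1 sets day 90 ± 7 and day 180 ± 14. If the last steroid dose falls on the first window day, the earliest deferred sample is:

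- Visit 2: 83 + 30 = day 113, against a window end of day 97
- Visit 3: 166 + 30 = day 196, against a window end of day 194

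With a 28-day month the results are day 111 and day 194, so Visit 3 just fits and Visit 2 does not. The text under Table 6-2 tolerates visits outside the window, but nothing says whether a deferred sample is analysed as the Visit 2 or Visit 3 sample.

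**The case against.** **The rule may have been meant more broadly.** Its waiting time mirrors inclusion criterion 4, and deferring a patient on day 5 of a course but not the day after would defeat its purpose. That is a fair reading of intent. Sites follow the text, however, and the text does not say it.

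**The numbers are small and are upper bounds.** Steroids are allowed only as clinically warranted, so not every relapse is treated, and the assumed rates have no source in the documents. This stands and limits the weight of the point.

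**Relapse and infection.** A reader might infer that Visit 2 and 3 samples should also meet the other entry conditions, "Last relapse of the patient should be at least 2 months before study entry" and the exclusion for "Presence of any clinically active infections". The documents do not support that. Neither condition is stated as a sampling standard for later visits, and the infection criterion may equally be there for safety. Relapse and infection on treatment are post-baseline events that the drug may influence. Keeping those samples is a legitimate comparison, while dropping them selects on outcome and favours responders.

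**An impossible window.** A reader might also infer that the deferral can never be met within the visit schedule. That is too strong, because the text under Table 6-2 softens the windows and the Visit 3 result turns on whether a month is 30 or 28 days. What remains is the missing statement of how a late sample is labelled.

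**Steroid data are already collected.** Protocol 5.4.6 sends steroid use to the CRF. This makes the remedy cheap, but it does not supply an analysis that uses the data.

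**Conclusion.** The point holds for corticosteroids. As written, the trigger leaves the 30 days after a course uncovered, against a one-month standard that the protocol itself uses, and the SAP has no step that would reveal the effect.

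It is a validity gap and not a demonstrated large bias. Under the assumptions above, about 1 to 5 of 60 patients are affected at a given visit for rates of 0.2 to 1.0, and mean IL-17 moves by about 0.1 to 1.2 pg/ml for rates of 0.1 to 1.0. The other markers and the flow cytometry results cannot be sized from the documents.

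A reader might infer that the primary objective is compromised. In its baseline form, Control vs Visit 1, it is not. Nor can a specific distortion of the secondary objective be shown, since the SAP gives no method for it. What can be said is that any such analysis would take in errors concentrated in relapsing patients.

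**What to change.** - **Protocol 5.4.6:** change the sampling trigger to a patient who *has received corticosteroids within the previous month*. This changes when blood is drawn, not how a relapse is treated.
- **Protocol 5.4.6, Table 6-1 and the visit-window text under Table 6-2:** reconcile them by stating that a sample deferred for this reason still counts as the Visit 2 or Visit 3 sample.
- **SAP 6.5.1 and 6.5.2:** keep all samples in the main contrasts. Add one pre-specified sensitivity analysis that excludes samples taken within one month of the last steroid dose, using the CRF steroid record. Confirm that the CRF captures the date of the last dose.
- **Optional:** describe how many Visit 2 and 3 samples followed a recent relapse or coincided with active infection. Excluding them is a trade-off and is not part of this fix.

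**Cost.** The change takes a reworded sentence, a clarification and one extra analysis. A few samples will be taken up to about a month late. At Visit 3 such a sample is separated from the same-day EDSS and functional tests. It also falls after the last scheduled dispensing, because Table 6-1 dispenses medication only at Visits 1 and 2 and ends the study at Visit 3. The sponsor must reconcile these passages. Where deferral is not practicable, the sensitivity analysis alone handles the problem.
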